10. One week before the operation, there are signs of infection, body temperature rises $>37.5^{\circ}\text{C}$, blood WBC $>10.0 \times 10^9/\text{L}$;
11. History of antibiotic use 1 week prior to surgery (excluding preoperative shock medication);
12. Preoperative neoadjuvant patients

(iii) Exit criteria

1. Accompanied by other non-oncological conditions that make it impossible for the patient to continue to receive this treatment plan;
2. After enrolment in the study, patients who required emergency surgery due to intestinal obstruction, perforation, or bleeding, et al. prior to stoma closure;
3. Patients with pathologically confirmed distant metastases after rectal surgery, including liver, pelvis, ovary, peritoneum, and distant lymph node metastases;
4. Intraoperative exploration for middle and low rectal cancer in anus-preserving surgery for those who need combined organ resection;
5. After enrolment in the study, patients requested to withdraw from the study cohort for various reasons, or were unable to complete the study programme and follow-up for various reasons;
6. Anastomotic fistula, severe anastomotic stenosis (inability to pass through enteroscopy or oesophageal finger and inability to dilate via oesophageal finger) after radical rectal surgery.

IV. Study endpoints

(i) Primary study endpoints:

Incidence of major LARS after 6 months of stoma closure.

(ii) Secondary research endpoints:

1. Bacteriological sequencing 1 month after stoma closure

[figure not shown]
2. Anorectal function (LARS questionnaire, Wexner¹⁵ incontinence score, MSKCC¹³⁻¹⁴ bowel function questionnaire), Glazer pelvic floor muscle surface electromyography, and quality of life scores after 1 month of stoma return.

3. Recovery of postoperative bowel function

After reversal surgery, time to oral feeding, time to anal defecation after reduction surgery, and rate of intestinal obstruction (intestinal obstruction was defined as ,inability to tolerate food for more than 72 H or the need for re-fasting or gastrointestinal decompression) were observed.

V. Research design

The study was a prospective randomised design with simple randomised grouping, randomised by prior computer-generated random number tables. The expected recruitment cut-off date for all subjects was 1 November 2022, with a predictable sample size of 60 cases to be enrolled based on patient admissions to the hospital. The enrolment process is as follows

(i) Transanal reinfusion of stoma discharge

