(1) Items: including LARS score, Wexner incontinence score, MSKCC bowel function questionnaire; quality of survival score. The questionnaire follow-up was conducted by a professional pelvic floor follow-up team. The investigators of the pelvic floor follow-up team had appropriate professional training and were unaware of the patient grouping. The method of answering the questionnaires was explained to the patients before the questionnaire assessment, and after detailed enquiry, the patients were asked to answer the questionnaires in a specific way.

(2) Time: before radical rectal surgery, 1 month after stoma closure, 3 months after stoma closure and 6 months after stoma closure.

Survival follow-up:

Patient survival at 1 year post-stoma closure, 2 years post-stoma closure, 3 years post-stoma closure, and 5 years post-stoma closure follow up.

VII. Observation indicators

1. Baseline information: gender, age, height, weight, ASA, past medical and treatment history, co-morbidities, laboratory tests and imaging.
2. Sequencing of intestinal flora: before radical rectal surgery, before stoma closure, and 1 month after stoma closure.
3. Perioperative period: also include time to first postoperative defecation, time to first postoperative semi-liquid diet, and incidence of postoperative intestinal obstruction.
4. Follow-up indicators: LARS syndrome score, Wexner score, MSKCC Bowel Function Questionnaire, QLQ-C30 Quality of Life Scale.

VIII. Signing of informed consent and registration of subjects

(i) Informed consent signing:

The study will be conducted in accordance with clinical trial protocols, GCP principles and the Declaration of Helsinki. The informed consent form will be signed by the PI or a qualified, trained and authorised clinical staff member. The trial process needs to be explained in detail to the subject and/or authorised person, and it is important to avoid over-informing and to give the subject and/or authorised person enough time to consider whether to participate or not. Subjects/authorised persons will be enrolled in the experimental group once they have agreed and signed the informed consent form. The original informed consent form is kept on file at the research centre and a copy is retained by the subject.

(ii) Subject registration

After signing the informed consent form, patients are registered with subject information, baseline data, and oncology-related data, which should include all data from the screening phase of this study.

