IX. Sample size calculation

The sample size was calculated using PASS 15 software, with the major LARS incidence rate at 6 months after stoma closure surgery as the primary outcome. Based on retrospective data from the authors' centre, the major LARS rate at 6 months after stoma closure surgery was estimated to be 14% in the stoma discharge reinfusion group and 47% in the control group. Thus, a sample size of 27 patients was required to achieve 80% power in detecting differences, with a two-sided level of significance of 0.05.

Assuming a dropout rate of up to 10%, 60 patients were enrolled.

X. Methods of statistical analysis

(i) Definition of analysis set

1. Full Analysis Set (FAS)

According to the basic principle of intentional analysis (ITT), all enrolled subjects who were given a randomisation number will be included in the FAS. the FAS is the primary dataset for the evaluation of the efficacy of this study.

2. Compliance with the programme set (Per-Protocol Set, PPS)

PPS is defined as all cases in which planned treatment and visits were completed as specified in the protocol and there were no protocol violations that significantly affected outcomes. Patients with protocol violations that significantly affect the protocol will be excluded from this analysis set. Protocol violations that significantly affect efficacy will be identified at the time of data review. PPS is a secondary data set for the efficacy evaluation of this study.

3. Safety Set (SS)

Cases that completed at least one safety evaluation data after enrolment constituted the safety population of this study. The safety population was the primary population for the safety evaluation of this study.

(ii) Methods of statistical analysis

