1. General principles: All statistical tests will be two-sided, and $P < 0.05$ will be considered statistically significant for the differences tested. The description of quantitative indicators will calculate the mean, standard deviation, median, minimum value, maximum value, if it meets the normal variance chi-square, expressed as the mean \pm standard deviation, and use the t-test to compare the differences between the two groups; data that do not meet the normal variance chi-square are expressed as the median (quartile), and the rank sum test is used for comparison. Categorical indicators were described by the number of cases and percentages in each category, and the chi-square test was used to compare the differences between the experimental and control groups.

2. The main outcome indicators of the occurrence of LARS at 6 months after the

reduction were expressed as the number of cases (percentage), and the chi-square test was used to compare the differences between the experimental group and the control group.

Secondary outcome indicator colony species results will be tabulated based on the top 15 species in abundance using cumulative histograms to compare species composition differences between samples. Based on the species abundance information of each sample at the genus level, the top 50 genera of abundance will be selected, and the samples and species will be clustered based on the abundance information of each sample, and heat maps will be drawn. And Shannon diversity index, Simpson index and Chao1 richness index were calculated for Alpha diversity analysis Comparative analysis of microbial community composition of samples between different groups was performed using Beta diversity analysis.

Secondary outcome indicators Wexner score, MSKCC Bowel Function Questionnaire, and QLQ-C30 Quality of Life Scale scores were analysed for repeated-measures data between the two groups, Mauchly's test of sphericity was performed, and ordinary one-way ANOVA or multifactorial ANOVA was performed according to the test results.

x. schedule of visits

| | | | | | | |
|---------------------------------------|--------------------------------------|-------------------|-------------------------------------|--------------------------------------|---------------------------------------|---------------------------------------|

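### The sphericity-tested ANOVA for Wexner, MSKCC and QLQ-C30 has no missing-data rule, so it defaults to patients with every visit complete, at odds with the all-randomised primary efficacy set

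*Combined protocol and SAP*

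**What the plan says.** **Method.** Section X(ii)2 gives one rule for three questionnaires: the Wexner, MSKCC and QLQ-C30 scores "were analysed for repeated-measures data between the two groups". It continues: "Mauchly's test of sphericity was performed, and ordinary one-way ANOVA or multifactorial ANOVA was performed according to the test results".

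**Visits.** Section VI collects the questionnaires at four times: "before radical rectal surgery, 1 month after stoma closure, 3 months after stoma closure and 6 months after stoma closure". The schedule of visits agrees.

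**Endpoint.** Section IV(ii)2 places the questionnaire endpoint at a single time, ending with "quality of life scores after 1 month of stoma return".

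**Analysis set.** Section X(i)1 states that "all enrolled subjects who were given a randomisation number will be included in the FAS" and that "the FAS is the primary dataset for the evaluation of the efficacy of this study". The per-protocol set, which requires completed visits, is given a secondary role.

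**Expected loss.** Section IX: "Assuming a dropout rate of up to 10%, 60 patients were enrolled". Section III(iii) also lists inability to complete follow-up among the exit criteria.

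Nowhere do the documents give a missing-data rule, an imputation method, a mixed model or a dedicated 1-month analysis for these scores.

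**The concern.** Mauchly's test is computed from the within-patient covariance across visits. The univariate repeated-measures ANOVA that it supports, and the multivariate test used when sphericity fails, both need a full row of visits for each patient. With no other instruction, a patient who lacks one score is deleted from the whole analysis.

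Two things are at stake. The first is consistency: the secondary questionnaire results would be labelled as full-set results but would rest on completers, which is close to the visit requirement that the plan reserves for its secondary set. The second is the 1-month result itself. If it is read off this model, valid 1-month forms are discarded because of something that happened at month 3 or 6. That costs precision in a 60-patient trial. It also biases the comparison if patients with poor early bowel function are the ones who later stop returning forms.

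**Working it through.** **1. The plan's own numbers.** Section IX assumes major LARS rates of 14% and 47%, two-sided 0.05 and 80% power. Allocation is taken as 1:1, which the plan does not state. With unpooled variance:

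n per arm = (1.960 + 0.842)² × (0.14×0.86 + 0.47×0.53) / 0.33² = 26.63, so 27.

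27 / 0.90 = 30 per arm, or 60 in total. Both figures reproduce, reading the stated 27 as per arm. The 10% is therefore a single allowance for total dropout, and it is the only loss rate in the documents.

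**2. Does the method need complete rows?** A standard repeated-measures ANOVA routine was given data with one visit missing for one patient. It refused to run because the data were unbalanced. The analyst must then delete the patient or improvise a rule.

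**3. Loss under the plan's own 10%.** If 10% drop out permanently, 60 × 0.90 = 54 patients are complete. Depending on when they leave, 54 to 60 have a 1-month form. At most 6 observed 1-month scores are lost, and the standard error ratio is at most √(60/54) = 1.05.

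**4. Loss under assumed intermittent non-response.** The documents give no per-visit rate, so m is an assumption, taken as independent across visits. Complete patients = 60(1−m)^k. Patients with a 1-month form = 60(1−m). The standard error ratio is the square root of the second over the first.

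| m per visit | Visits at risk | Complete | With 1-month form | SE ratio |
|---|---|---|---|---|
| 5% | 3 post-closure | 51.4 | 57 | 1.05 |
| 10% | 3 post-closure | 43.7 | 54 | 1.11 |
| 5% | 4, with pre-surgery | 48.9 | 57 | 1.08 |
| 10% | 4, with pre-surgery | 39.4 | 54 | 1.17 |

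The three-visit rows are the more realistic, because the pre-surgery form is collected before any follow-up loss.

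**5. Bias.** This was simulated with 30 per arm, a true 1-month difference of 0.75 SD, and the chance of missing the 6-month form logistic in the 1-month score. All of these inputs except the arm size are assumptions.

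| Log-odds per SD | Missing | Completers' 1-month difference | Bias |
|---|---|---|---|
| 0.5 | 10% | about 0.73-0.74 | 0.01-0.02 |
| 1.0 | about 13% | about 0.69 | 0.06 |
| 1.5 | about 13% | about 0.65 | 0.10 |

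Using every observed 1-month score gives 0.75 in each case. For scale, the standard error of the difference with 30 per arm is √(2/30) = 0.26 SD.

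**The case against.** **The plan does not say completers only.** This is correct. A reader might infer that the plan prescribes a complete-case analysis, but that restriction is a property of the named method. The documents are silent on missing data and do not say which visits enter the model. What stands is that the default has not been overridden.

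**The wording could mean something else.** The reference to an ordinary one-way ANOVA could describe a separate test at each visit. The general principles in Section X(ii)1 also offer a t-test or rank-sum test for quantitative indicators. Either would keep every 1-month form. This cannot be excluded, so a reader who concludes that the 1-month endpoint certainly loses patients goes further than the text. The reading is still less likely: Mauchly's test has no part in choosing a single-visit test, and a specific sentence for these scores would normally govern over a general rule.

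**The loss may be small.** This also stands. A fall to 49 or 39 patients needs 5% or 10% loss at each of four visits, including the pre-surgery form. That leaves 19% or 34% of patients incomplete, against the plan's single allowance of 10%. The largest bias shown is under half of one standard error and needs strong informative missingness.

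**A mixed model does not restore the full set.** It cannot use patients with no post-closure score, including those who leave before closure under the exit criteria in Section III(iii). This is a limit of the remedy, but it does not favour the ANOVA, which loses the same patients and others besides.

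**Conclusion.** The concern holds as a gap in the secondary analyses. The method named for the three questionnaires analyses only patients complete at every visit entered, on its most natural reading. No missing-data rule changes that, and the result conflicts with the all-randomised set named as primary for efficacy. Loss of patients from the 1-month endpoint follows if that comparison is taken from this model, which is likely but not certain.

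On the plan's own figure the cost is limited: at most 6 observed 1-month scores and about 5% in standard error. Under assumed post-closure non-response of 5% or 10% per visit, the standard error is about 5% or 11% larger. Bias ranges from negligible to about 0.10 SD on 0.75 SD, depending entirely on assumed informative missingness.

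A reader might extend this to the trial's main result. The documents do not support that: major LARS at 6 months is compared by a separate chi-square test that does not pass through this ANOVA. The change is still worth making, because it is cheap and keeps data that the trial will already have collected.

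**What to change.** In Section X(ii)2, replace the Mauchly-directed ANOVA for Wexner, MSKCC and QLQ-C30 with a linear mixed model for repeated measures. Include arm, visit and arm-by-visit terms with an unstructured covariance. Fit it to all observed scores from randomised patients with at least one post-closure score. Pre-specify the arm difference at 1 month from this model as the secondary comparison, and keep the completers' ANOVA as supporting only. Report by arm how many randomised patients have no post-closure score, because the model does not recover them.

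The cost is a rewritten paragraph and standard software, with no new patients, visits or data. The model assumes that missingness is explained by the observed scores. That should be stated, but it is a weaker assumption than the completers' analysis makes. If the sponsor intended separate tests at each visit, the section should say so and drop the reference to Mauchly's test.

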| sports event | Pre-radi cal rectal surgery | pre-discha rge | Pre-sto ma closure surgery | Post-sto ma closure 1 month | Post-sto ma closure 3 months | Post-sto ma closure 6 months |
| Demographic information | ✓ | | | | | |
| Baseline assessment | ✓ | | | | | |
| bacterial colony sequencing | ✓ | | ✓ | ✓ | | |
| Pelvic floor muscle examination | ✓ | | ✓ | ✓ | ✓ | ✓ |
| surgical treatment | | ✓ | | | | |
| postoperative pathology | | ✓ | | | | |
| postoperative follow-up | | | | ✓ | ✓ | ✓ |

| | | | | | | |
|--|---|--|---|---|---|---|
| rectal examination | | | ✓ | ✓ | ✓ | ✓ |
| Pelvic floor surface electromyography assessment | ✓ | | ✓ | ✓ | ✓ | ✓ |
| Functioning, quality of life questionnaire | ✓ | | | ✓ | ✓ | ✓ |

Schedule 1

LARS Bowel Function Questionnaire

Does the patient complain of abnormal bowel movements: Yes No
Patient complained of abnormal defecation as: increased frequency incontinence painful defecation inability to distinguish between gas and faeces other

Whether the patient is satisfied with the current state of defecation:
Satisfied Unsatisfied

Does the patient think that the current state of defecation affects daily life:

No effect Yes effect

Use of medication to improve bowel movements: Yes Name _____ No

Prophylactic fistula Yes No

Prophylactic Fistula Payback Time is time Year Month Day
No

1. Have you ever had uncontrollable flatulence (farting)?

| | |
|--------------------------------|---|
|  Never | 0 |
| points | |
| Yes, less than 1 time per week | 4 |
| points | |
| Yes, at least once a week | 7 |
| points | |

2. Have you ever had an accidental leakage of loose stool?

| | |
|--------------------------------|---|
|  Never | 0 |
| points | |
| Yes, less than 1 time per week | 3 |
| points | |
| Yes, at least once a week | 3 |
| points | |

3. How many times a day do you have a bowel movement?

| | |
|---|---|
|  More than 7 times per day (24 hours) | 4 |
| points | |
|  4~7 times per day (24 hours) | 2 |
| points | |
|  1~3 times per day (24 hours) | 0 |
| points | |
|  Less than 1 time per day (24 hours) | 5 |

points

4. Have you ever had to have another bowel movement within an hour of having one?

Never

0

points

Yes, less than 1 time per week

9 points

Yes, at least once a week

11

points

5. Have you ever had to flush to the loo because of an urgent bowel movement?

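### Mauchly's test cannot choose the between-arm analysis of the Wexner, MSKCC and QLQ-C30 scores, and the plan does not say whether the 1-month or the all-visit arm effect is the endpoint result

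*Combined protocol and SAP*

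**What the plan says.** Four parts of the combined protocol and SAP bear on this point.

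- **Section IV (ii) 2** lists the functional scores as secondary endpoints at a single time, ending "and quality of life scores after 1 month of stoma return".
- **Section VI (2)** collects the questionnaires at four times: "before radical rectal surgery, 1 month after stoma closure, 3 months after stoma closure and 6 months after stoma closure". The visit schedule agrees, in its row "Functioning, quality of life questionnaire".
- **Section X (ii) 2** says that the Wexner, MSKCC and QLQ-C30 "scores were analysed for repeated-measures data between the two groups", and then that "Mauchly's test of sphericity was performed, and ordinary one-way ANOVA or multifactorial ANOVA was performed according to the test results".
- **Section X (ii) 1** gives a general rule for quantitative measures: "use the t-test to compare the differences between the two groups" or, if the assumptions fail, "the rank sum test is used for comparison". It names no visit.

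The plan does not say which Mauchly result leads to which ANOVA, what the factors are, or which effect is tested. It gives the pre-surgery score no role.

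**The concern.** Mauchly's test examines the covariance of the differences between visits within patients. Its result can guide the choice between an uncorrected and a corrected test of visit and arm-by-visit, or between a univariate and a multivariate one. It cannot tell an analyst whether to use one factor or several, and it has no bearing on the comparison between the arms. Two analysts following Section X could therefore run different analyses.

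The endpoint and its analysis also do not meet. Section IV points to 1 month and Section X to the repeated visits. If the choice of result is made after the data are seen, there are two chances of a significant finding instead of one, and the two answers can differ.

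**Working it through.** **Plan's own figures.** The plan gives no effect size, SD or correlation for these scores. The only design figure to reproduce is the primary sample size in Section IX (14% against 47%, two-sided 0.05, 80% power). With unpooled variance:

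n = (1.960 + 0.842)² × (0.14×0.86 + 0.47×0.53) / 0.33² = 7.85 × 0.3695 / 0.1089 = 26.6, so 27 per arm. Then 27/0.9 = 30 per arm, or 60 in all.

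This matches the plan and supports reading 27 as per arm. It is used below only as the number of patients.

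**Step 1. Does sphericity touch the arm comparison?** In a two-arm repeated-measures ANOVA with equal visit weights, the arm test is a t-test on each patient's mean over visits, with 2×27 − 2 = 52 degrees of freedom. A 1-month comparison is a t-test on one score per patient. No within-patient contrast enters either. A null simulation (30 per arm, 4,000 runs per setting) agrees. With four visits and first-order autoregressive correlation 0.7, Mauchly's test rejected in 98.5% of trials, while the arm test rejected in 5.1%. Over all settings the arm test stayed between 4.2% and 5.5%.

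**Step 2. What does the missing choice cost?** Assume 27 per arm, visits at 1, 3 and 6 months, unit SD, normal scores and equal correlation r between visits. The SD of a patient's mean is √((1+2r)/3). This is also the correlation between the 1-month and all-visit arm estimates. Null rates are from 100,000 simulated trials:

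| r | Correlation of the two estimates | 1-month test alone | All-visit test alone | Either significant |
|---|---|---|---|---|
| 0.3 | √(1.6/3) = 0.730 | 0.051 | 0.050 | 0.083 |
| 0.5 | √(2.0/3) = 0.816 | 0.050 | 0.050 | 0.077 |
| 0.7 | √(2.4/3) = 0.894 | 0.049 | 0.050 | 0.070 |

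Under autoregressive correlation the last column is 0.086, 0.081 and 0.076. Each test is sound alone; the excess comes only from leaving the choice open.

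**Step 3. Which effect has more power?** The non-centrality is (effect/SD) × √(27/2). For 0.7 SD at 1 month it is 0.7 × 3.674 = 2.572, giving power 0.714. For a constant 0.7 SD over all visits it is 2.572 divided by 0.730, 0.816 or 0.894, giving 0.933, 0.871 and 0.806. Other assumed time courses:

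| Effect at 1, 3, 6 months (SD) | Power at 1 month | All-visit power, r = 0.3/0.5/0.7 |
|---|---|---|
| 0.7, 0.7, 0.7 | 0.71 | 0.93 / 0.87 / 0.81 |
| 0.35, 0.525, 0.7 | 0.24 | 0.74 / 0.64 / 0.56 |
| 0.7, 0.525, 0.35 | 0.71 | 0.74 / 0.64 / 0.56 |
| 0.7, 0.35, 0 | 0.71 | 0.41 / 0.34 / 0.29 |

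Neither effect is better in general.

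**Step 4. What is the pre-surgery score worth?** With it as covariate, simulated power at 1 month (0.7 SD; 0.71 unadjusted) is 0.70, 0.71, 0.72, 0.74, 0.82 and 0.94 at assumed baseline correlations of 0, 0.1, 0.2, 0.3, 0.5 and 0.7.

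**The case against.** The best defence is that the text is visibly a rough translation: the same section speaks of a normal variance chi-square, and the visit table is headed as a sports event. Univariate or multivariate repeated-measures ANOVA is a natural source for the phrase and a legitimate use of Mauchly's test. That stands, and the first part may be no more than a terminology correction. It does not settle which arm effect is reported.

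A reader might infer four stronger things, which the documents do not support:

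- **That visits will be pooled as independent records.** Type I error would then be 0.12-0.21 with three visits and 0.16-0.27 with four. But Section X calls these repeated-measures data, so that reading is unlikely and its figures should not set the severity.
- **That any of three or four tests may count.** This would give 0.115-0.127. It needs the general t-test or rank-sum rule, or the arm-by-visit test, to compete as the result. Ordinarily the specific rule for these scores overrides the general one, so the relevant range is the 0.07-0.08 above.
- **That a 1-month comparison is absent.** A per-visit ANOVA or the general rule can supply it. What is missing is its status.
- **That the two results will usually conflict.** In the constant-effect case they disagree in 14-24% of simulated trials, and under the null in 4-6%. Larger figures depend on assumed time courses.

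Leaving out the pre-surgery score is also valid. Using it is a possible gain in precision, not the repair of an error.

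**Conclusion.** The concern holds, with minor impact. As worded, the Mauchly rule cannot select the between-arm analysis, although a valid meaning may lie behind it. On either reading the plan does not say whether the 1-month or the all-visit arm effect answers the Section IV endpoint. If either may count, the false-positive rate for each score is about 0.07-0.08 instead of 0.05. That figure assumes 27 per arm, three post-closure visits, normal scores and within-patient correlation of 0.3-0.7; the documents give none of the score properties. If the Section IV wording was meant as from 1 month onward, that too has to be stated. The primary chi-square test of major LARS at 6 months is unaffected.

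**What to change.** Delete the Mauchly-based choice in Section X (ii) 2 and replace it with wording such as:

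*Wexner, MSKCC and QLQ-C30 scores at 1, 3 and 6 months are analysed with the patient as the unit in a repeated-measures model with arm, visit, arm-by-visit and the pre-surgery score as covariate. The arm difference at 1 month, with its 95% confidence interval, is the secondary endpoint result. The 3- and 6-month differences and the arm-by-visit test are supportive.*

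A linear mixed model or a sphericity-corrected repeated-measures ANOVA would serve. If the sponsor prefers the all-visit effect, Section IV should be changed to match before any scores are compared by arm.

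Also state which Wexner instrument is analysed. Sections IV (ii) 2 and VI (1) name the incontinence score, while Schedule 4 is headed as the constipation score. Name the MSKCC score too, since Schedule 5 lists three-category items without a scoring rule.

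**Cost.** This is a wording change using data already scheduled. Naming 1 month gives up power if the effect is constant (0.71 against 0.81-0.93 at an assumed 0.7 SD) or rising. It gains power if the effect fades to nothing, and is about even or better if it halves. The covariate costs about 0.01 power if the baseline correlation is 0.

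The mixed model keeps patients with some post-closure scores, whereas the classical ANOVA drops anyone who misses a visit. That is closer to a FAS in which "all enrolled subjects who were given a randomisation number will be included in the FAS", but only in part: patients who exit before closure and have no later score are not recovered, and those without a pre-surgery score drop out unless it is imputed.

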| Sometimes | 2  | 0 | 0  |
| Usually | 3  | 1-5 | 1  |
| Always | 4  | 5-10 | 2  |
| | | 10-20 | 3  |
| | | More than 20 | 4  |
| Total Score: _____ | | | |

Schedule 5:

| Bowel symptoms (MSKCC Bowel Function Questionnaire) | Always/often | Sometimes/rarely | non-occurrence |
|---|--------------|------------------|----------------|
| constipation | | | |
| When you feel like having a bowel movement, can you wait 15min before going to the toilet? | | | |
| Do you have another bowel movement within 15 minutes after the previous one? | | | |
| Are your bowel function issues affecting your daily activities? | | | |
| During the day, do you ever use tissues, nappies or pads under your underwear to prevent leakage? | | | |
| Have you ever had loose stools? (Slightly formed, paste-like) | | | |
| Have you ever soiled your underwear during the day? | | | |
| Have you ever had diarrhoea? (unformed, watery stools) | | | |
| Have you ever soiled (leaked) your underwear while sleeping? | | | |
| Have you ever used medication (e.g. diarrhoea, antidiarrhoea) to reduce the frequency of bowel movements? | | | |
| Bowel movements are affected by diet | | | |
| Have you ever controlled your bowel movements by limiting the types of solid foods you consume? | | | |
| Does the intake of certain solid foods increase the number of bowel movements per day? | | | |
| Have you ever controlled your bowel movements by limiting the types of liquid foods you consume? | | | |
| Does drinking a certain liquid increase the number of bowel movements per purpose? | | | |
| Abnormal bowel movements | | | |

| | | | |
|--|--|--|--|
| Do you go to the toilet regularly? | | | |
| Do you feel like you have completely emptied your bowels after a bowel movement? | | | |
| Can you control your bowel movements? | | | |
| Do you know the difference between the sensation of having to pass gas (fart) and having a bowel movement? | | | |

bibliography

1. Zheng Rongshou, Zhang S, Sun KX. Analysis of malignant tumour prevalence in China in 2015. *Chinese Journal of Oncology*. 2019;41(1):19-27.

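### Schedule 5 merges MSKCC response frequencies into columns that cannot be separated later, and the plan states no scoring or item-direction rule for the MSKCC scores analysed in Section X

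*Combined protocol and SAP*

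**What the plan says.** Section IV lists the questionnaire among the secondary endpoints: "Anorectal function (LARS questionnaire, Wexner¹⁵ incontinence score, MSKCC¹³⁻¹⁴ bowel function questionnaire". Section VI schedules it four times: before radical surgery and at 1, 3 and 6 months after stoma closure. Section X (Methods of statistical analysis) treats the result as a numerical score: "Wexner score, MSKCC Bowel Function Questionnaire, and QLQ-C30 Quality of Life Scale scores were analysed for repeated-measures data". ANOVA follows a test of sphericity.

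Schedule 5 is the only MSKCC form in the document. Its header reads "Bowel symptoms (MSKCC Bowel Function Questionnaire) | Always/often | Sometimes/rarely | non-occurrence". It prints no points, total line, subscale rule or reversal instruction, and Section X adds none. The other two attached bowel questionnaires differ: Schedule 1 (LARS) has item points, a summing rule and cut-offs, and Schedule 4 (Wexner) has item points and a total line.

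Item wording runs in both directions. Frequent occurrence is good for "When you feel like having a bowel movement, can you wait 15min before going to the toilet", "Do you feel like you have completely emptied your bowels after a bowel movement" and "Can you control your bowel movements". It is bad for "Have you ever soiled your underwear during the day".

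**The concern.** There are two separate problems, and they differ in whether they can be undone.

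The first is at data capture. The header names five frequencies but offers three boxes. A patient who moves from always to often, or from sometimes to rarely, records no change. If the scoring that the plan intends needs those levels, no later step can supply them.

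The second is at analysis. A score is to be compared between arms, but the plan does not say how ticks become numbers, which items are reversed, or whether a total or subscales are meant. If that is left open, the choices may be made after the data have been seen. Adding all items in one direction would let good-function items offset symptom items. The last block makes this easy to do by accident: four questions, all of them positively worded if regular toilet use counts as good, stand under a heading about abnormal bowel movements.

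**Working it through.** **The plan's own figure.** The plan gives no figure for the MSKCC score. Its only calculated figure is the sample size for major LARS (Section IX), which does not use this form. It reproduces with an unpooled normal approximation: (1.960 + 0.842)² × (0.14 × 0.86 + 0.47 × 0.53) / 0.33² = 26.63, so 27 per group, and 54 / 0.90 = 60.

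**Levels lost.** The header names, in order: always, often, sometimes, rarely, non-occurrence. Five ordered levels have four adjacent boundaries. The form keeps two (often versus sometimes, rarely versus non-occurrence) and drops two (always versus often, sometimes versus rarely). The documents give no response distribution, so the resulting loss of precision cannot be put as a number.

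**Item count.** Three rows of Schedule 5 (constipation, effect of diet, abnormal bowel movements) are read as headings. That leaves 9 + 4 + 4 = 17 items. Always is good for five: waiting 15 minutes, regular toilet use, complete emptying, control, and telling gas from stool. Regular toilet use is arguable, so the count is 5 good and 12 bad, or 4 good and 13 bad.

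**Range of a total.** Assume codes of 2, 1 and 0 from left to right; the plan states none. Let k be the number of good-direction items.

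- With reversal: best 0, worst 2 × 17 = 34, span 34.
- Without reversal: best = 2k, worst = 2(17 − k), span = 34 − 4k.
- k = 5: best 10, worst 24, span 14; 14/34 = 41%.
- k = 4: best 8, worst 26, span 18; 18/34 = 53%.

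**By block, without reversal, k = 5.**

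| Block | Items | Good-direction items | Best function | Worst function |
|---|---|---|---|---|
| First | 9 | 1 | 2 | 16 |
| Diet | 4 | 0 | 0 | 8 |
| Last | 4 | 4 | 8 | 0 |
| Total | 17 | 5 | 10 | 24 |

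The last block runs opposite to the other two, so using subscales instead of a total does not remove the need for a stated direction.

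**Sensitivity.** Codes of 3/2/1 shift the totals (27 to 41 unreversed, 17 to 51 reversed) but leave the spans at 14 and 34. If the constipation row is an item, there are 18 items with 13 bad and 5 good. The unreversed total then runs from 10 to 26, a span of 16 out of 36, and the conclusion is the same.

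**The case against.** The strongest objections concern how far the point reaches, and several of them stand.

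- *A reader might infer that no valid MSKCC score can be formed from this form.* The documents do not support that. Mixed item direction is not a defect in itself. The tick and the item wording are both on the page, so items can be reversed at analysis and a consistent three-level score built from forms already collected.
- *A reader might infer from the ranges that about half of any difference between arms is lost.* That does not follow. The plan states no unreversed sum. The share lost depends on which items differ between arms; if only soiling or diet items differ, none is lost. If items move together, the standard deviation shrinks with the range and the test statistic changes little.
- *A reader might infer that the cited instrument has five response levels.* The documents do not say so. The paired labels suggest merging, but the scoring in the two cited references is not reproduced here.
- The absence of a printed key does not show that none will be used. QLQ-C30 scores are also analysed with no form attached, so the plan may rely on established scoring. This is fair, but the plan does not say that it applies a published MSKCC key, or that such a key suits a three-column form.
- Data collection may be well advanced: Section V expected recruitment to close on 1 November 2022, and Section IX says that 60 patients were enrolled. Changing the form between visits could mix formats within patients. This limits the remedy.

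None of these answers the capture problem. The form names distinctions and then discards them. Separate columns can always be collapsed to three; three cannot be expanded to five.

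**Conclusion.** The point holds in two parts. The merged columns permanently remove two of the four adjacent distinctions that the form itself names, and any key needing them cannot be used. This rests only on the printed header. Its cost in precision cannot be quantified from the documents.

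The missing codes, reversals and score direction leave the MSKCC score in Section X undefined. The compressed span of 14 to 18 out of 34 points shows what an unreversed total would do. It is a bound on range under an assumed coding, with 17 items of which 4 or 5 run in the good direction. It is not an estimate of lost effect, and a reversal rule removes it entirely.

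Only a secondary endpoint is affected. Major LARS, its scoring and the sample size are unchanged.

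**What to change.** 1. Check the response levels and scoring of the cited MSKCC instrument. If the named frequencies match its levels, print Schedule 5 with a separate column for each (always, often, sometimes, rarely, non-occurrence) for forms not yet completed. If the cited scoring uses three levels, say so and keep the form.
2. In Section X, before analysis, state the code for each response, the reversed items (waiting 15 minutes, complete emptying, control, telling gas from stool, and a decision on regular toilet use), whether a total or subscales are analysed, the score range, and which direction means better function.
3. Flag every form completed in three columns. If formats are mixed within patients, base the main MSKCC comparison on the collapsed three-level, reverse-coded score.

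The cost is one revised form and a few lines of text. The downside is mixed formats if the form changes part-way, which step 3 handles. If collection is complete, only step 2 remains, with a statement that the data have three levels.
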